7.0 Statistical Considerations

Primary endpoint

The study is designed to evaluate the overall complication rate post-tissue expander reconstruction surgery using different types of mesh. Patients who are eligible for the study will be equally randomized to the following arms: 1) Alloderm; 2) Surgimend. The primary endpoint, overall complication after tissue expander implant is defined as any of the following complications: seroma; infection; implant malposition; capsular contracture; and, hematoma.

Sample Size

Patients who are seen at MDACC for immediate breast reconstructive surgery after mastectomy will be enrolled to the study and equally randomized to the two arms when the tissue expander is implanted: 1) Alloderm; 2) Surgimend. The randomization will be stratified by surgeon in order to avoid confounding between surgeon and surgical method. A total of 398 patients will be enrolled with 199 patients for each arm. The information on overall complication observed after tissue expander implant and before

the permanent implant will be collected. The rate of overall complication for the patients using Alloderm mesh (arm 1) will be compared to the patients using Surgimend mesh (arm 2). With 199 patients in each arm the study will have 80% power to detect the difference in complication rate between 10% in the Alloderm mesh group and 20% in the Surgimend mesh group with a two-sided type I error rate of 0.05 (calculated by nQuery Advisor 7.0). The secondary objective is esthetic evaluation. The main question for the esthetic evaluation is whether the overall shape of the reconstructed breast is good. Evaluators who are blinded to the arm assignment information will grade the patients using a 5-point Likert scale (strongly disagree, disagree, somewhat agree, agree, strongly agree). Their scores will be averaged for each patient.

Analysis Plans

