Patient information including age, BMI, smoking history, tumor size and location, breast size, mastectomy method, mastectomy surgeon, plastic reconstruction surgeon, quality of skin, tissue expander type, intraoperative fill volume, method of lower pole expansion, chemotherapy, and radiation therapy will be summarized. Outcome variables which include complications and scores for esthetic evaluation will be studied. Summary statistics including mean, standard deviation, median, and range will be provided for continuous variables (such as age and BMI) while frequency counts and percentages will be provided for categorical variables (such as smoking history and tissue expander type). The overall complication rate for each arm will be calculated along with the 95% confidence intervals. Fisher's exact test or the Chi-square test will be used to evaluate the association between two categorical variables. Cochran-Mantel-Haenszel test will be used to assess the association between treatment and outcomes by adjusting the stratification of surgeon's experience (≤ 3 years and >3 years). Logistical regression model will be used to assess the effect of patient variables on overall complication. For each question of the esthetic evaluation, an average score will be calculated for each patient based on the scores from all evaluators. Summary statistics for the scores including mean, standard deviation, median, and range will be calculated. The scores will be compared between the two mesh arms using Wilcoxon rank sum test.

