8.0 Data Collection

All population variables will be collected after enrollment in the study and prior to surgery. After the initial surgery, during which operative variables will be documented by the surgical team, patient data will be collected in clinic. At the postoperative week 1 visit, the patient will be assessed by the surgical team for incisional complications and mastectomy flap necrosis. At the postoperative week 2 visit, expansion will begin, absent complications preventing expansion. The patient will return to clinic for additional expansion, as determined by the a member of the surgical team, until the desired volume is reached. During each of these visits, the patient will be assessed for seroma and infection. After expansion, the patient will return in approximately 3 months for a preoperative visit, followed shortly by tissue expander exchange for a permanent implant. One to twelve months following implant exchange, 5 photographs

(standardized photographic views) will be taken and used for aesthetic evaluation (see Appendix D). Unique study numbers will be assigned to the photographs.

Population variables:

- age
- BMI
- breast size
- past medical history
- smoking history
- tumor size and location
- mastectomy surgeon
- mastectomy method

Operative Variables – These will be collected from the operative note or at the time of surgery:

- plastic/reconstructive surgeon
- tissue expander
- expander type
- quality of skin
- additional skin resection
- intraoperative fill volume
- method of lower pole expansion
- drains

Postoperative Variables – These will be recorded at clinic visits or retrospectively from clinic notes:

- duration of drains
- chemotherapy
- radiation therapy (out of study)
- number of post-op visits
- time to first expansion
- number of expansions
- final fill volume
- time to exchange
- type and volume of implant placed
- contralateral procedures performed
- nipple (yes/no)

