9.0 Outcome

The primary endpoint, overall complication after tissue expander implant is defined as any of the following complications: seroma, cellulitis, abscess, red breast syndrome, implant malposition, capsular contracture, and hematoma. These will be defined as follows:

Seroma: Any suspected fluid collection that is either radiologically confirmed by ultrasound or clinically confirmed by drainage, or both.

Cellulitis: Any redness of the breast that resolves with antibiotics, or requires surgical removal of implant, but does not contain a purulent fluid collection.

Abscess: Any purulent fluid collection confirmed during surgical removal of implant.

Red breast syndrome: Any prolonged redness of the breast, without other symptoms of infection, which does not resolve with antibiotics, and does not go on to require removal of the implant.

Malposition: Any surgeon perceived, postoperative movement of the expander outside of the surgically created pocket.

Capsular Contracture: Any postoperative capsule formation, classified according to the Baker classification, as follows: Baker 1: normal breast; Baker 2: palpable, minimally firm capsule; Baker 3: visible, easily palpated, moderately firm capsule; Baker 4: painful, hard and breast distorted.

Hematoma: Any postoperative collection of blood requiring surgical drainage.

Secondary endpoints are related to esthetic evaluation of postoperative, standardized five (5) view clinical photos.

Esthetic Evaluation

The esthetic evaluation will be based on five standardized photographic views: frontal; right lateral; left lateral; right three-quarter: and, left three-quarter. Photographs will be taken against a blue background, standard in all clinic rooms, at a distance of five feet from the patient.

Evaluators will include three attending plastic surgeons who are not taking care of any patients in the study, three plastic surgery fellows, and three physician assistants. Their scores will be averaged for each statement. Unilaterals and bilaterals will be judged separately.

Questionnaires will evaluate the breast esthetics based on a 1 to 5 scale (strongly disagree, disagree, somewhat agree, agree, strongly agree) of the following statements:

1. The overall shape of the reconstructed breast is good.
2. The overall symmetry with the other breast is good.
3. The upper pole transition is natural in appearance.
4. The lower pole has adequate fullness and ptosis.

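### The rank sum test of the esthetic scores is valid but ignores laterality; a van Elteren test stratified by laterality and surgeon experience would be a cheap, optional improvement

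*Combined protocol and SAP*

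**What the plan says.** The Analysis Plans in section 7.0 average each esthetic item over all evaluators for each patient, then state: "The scores will be compared between the two mesh arms using Wilcoxon rank sum test". No stratification is attached to that sentence. The Sample Size text in the same section names overall shape of the reconstructed breast as the main esthetic question.

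Two factors are treated as mattering elsewhere in the plan.

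- **Laterality.** Section 9.0, Esthetic Evaluation: "Unilaterals and bilaterals will be judged separately". Item 2 of the questionnaire reads "The overall symmetry with the other breast is good". Section 7.0 does not mention laterality, and the variable lists in sections 5.0 and 8.0 do not name it; contralateral procedures are the nearest entry.
- **Surgeon.** Section 7.0, Sample Size: "The randomization will be stratified by surgeon in order to avoid confounding between surgeon and surgical method". The Analysis Plans add a CMH test to "assess the association between treatment and outcomes by adjusting the stratification of" surgeon experience, in two groups (≤3 and >3 years). Shortly before, they say: "Outcome variables which include complications and scores for esthetic evaluation will be studied". The word outcomes in the CMH sentence can therefore be read to include the scores.

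**The concern.** If unilateral and bilateral patients score at different levels, a pooled ranking puts that difference into the noise against which the meshes are compared. A gap is plausible for the symmetry item: the other breast is not a reconstruction in a unilateral case and is one in a bilateral case. If the two groups are also rated in separate sets, evaluators may use different reference points.

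The text leaves three readings open: separate rating followed by one pooled test, separate rating with some stratified test, or two separate tests. They differ in power, and the third also differs in false-positive risk. At stake is the efficiency and clarity of the comparison that answers the secondary objective. The primary endpoint is not affected.

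**Working it through.** **The plan's own figure.** The only sample size stated is for complications, 10% vs 20%, two-sided 0.05, 80% power. With pooled variance, n = [1.960·√(2·0.15·0.85) + 0.842·√(0.09 + 0.16)]² / 0.10² = 198.96, so 199 per arm. It reproduces and is untouched by this point. No power is claimed for the esthetic scores.

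**Assumed inputs.** From the plan: 398 patients, 1:1 allocation, randomization stratified by surgeon, two experience groups. The two-sided 0.05 level is the plan's level for the primary endpoint. Assumed: mesh effect of 0.3 within-stratum SD, bilateral share, size of the laterality and experience gaps, number of surgeons, and a score for every patient.

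**Closed-form approximation.** With normal scores, the Wilcoxon noncentrality is λ = 0.3·√(199/2)·√(3/π) = 2.924, and power is Φ(2.924 − 1.96) = 83.3%. A stratified test stays near this value. For a laterality gap g and bilateral share b, pooling inflates the variance to 1 + b(1−b)g², so λ is divided by its square root. At g = 1:

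- b = 0.5: variance 1.25, λ = 2.616, power 74.4%; 8.9 points lost.
- b = 0.3: variance 1.21, λ = 2.658, power 75.8%; 7.5 points lost.
- b = 0.1: variance 1.09, λ = 2.801, power 80.0%; 3.3 points lost.

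At g = 0.5 pooled power is 81.0%, 81.3% and 82.4% for the same shares, a loss of about 1–2 points.

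**Simulation.** 4,000 runs per cell, 10 equal-volume surgeons (3 with ≤3 years), allocation balanced within surgeon, normal scores, van Elteren weights 1/(N_h+1), four strata. Monte Carlo error is about 0.6–0.7 points. Each cell gives power in percent, pooled → stratified.

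| Bilateral share | Experience gap (SD) | Laterality gap 0 | 0.25 SD | 0.5 SD | 1 SD |
|---|---|---|---|---|---|
| 50% | 0 | 83.4 → 83.0 | 81.3 → 81.2 | 81.2 → 82.6 | 73.5 → 82.7 |
| 50% | 0.5 | 81.7 → 82.8 | 80.3 → 81.7 | 79.1 → 82.4 | 71.0 → 82.5 |
| 30% | 0 | 83.1 → 82.9 | 81.8 → 82.1 | 81.0 → 82.4 | 75.0 → 82.5 |
| 30% | 0.5 | 81.8 → 82.4 | 80.4 → 82.2 | 80.0 → 83.0 | 74.1 → 82.7 |

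With 10% bilateral and 10% less experienced, the figures are 81.8 → 81.5 at no laterality gap and 79.4 → 81.9 at 1 SD. For averages of nine 1–5 ratings at 50% bilateral they are 78.6 → 78.6, 78.1 → 79.7 and 70.4 → 79.0 at gaps of 0, 0.5 and 1 SD.

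**Which factor does the work.** At 50% bilateral, a 1 SD laterality gap and no experience gap, power is 73.5% pooled, 73.7% stratified by experience only, 82.8% by laterality only and 82.7% by both. With a 0.5 SD experience gap, adding experience to laterality gains about 1 point (81.5% to 82.5% in the same column).

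**Second simulation, different assumptions.** 3,000 runs, 8 surgeons, 40% bilateral, effect 0.287 SD, scores rounded to ninths. No gaps: 79.8 → 79.1. Laterality 0.5 SD alone: 77.1 → 78.1. Both 0.5 SD: 76.5 → 80.2. Laterality 1 SD alone: 69.5 → 79.0. Both 1 SD: 63.2 → 79.0.

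**Type I error.** For laterality gaps up to 1 SD and experience gaps up to 0.5 SD with normal scores, pooled 3.9–5.3% and stratified 4.3–5.5%. With a 1 SD experience gap the pooled test is conservative (3.3%).

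**Two separate tests instead.** λ scales with the square root of the group's share: 2.924·√0.5 = 2.068 gives 54% power in each half. At 30% bilateral it is 69% (unilateral, λ = 2.447) and 36% (bilateral, λ = 1.602). Two unadjusted tests carry a 1 − 0.95² = 9.75% chance of at least one false positive.

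**The case against.** The strongest reply is that nothing is broken: a rank sum test under 1:1 randomization is valid, the endpoint is secondary, and the documents claim no power for it. That stands, and it keeps this point at low priority.

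Four further objections carry weight.

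- **The main question is overall shape, not symmetry.** The documents give no reason to expect a laterality gap in overall shape, let alone one of 1 SD. This stands; the gain on the main question may be nil.
- **Experience adjustment may already be planned.** The scores are listed as outcome variables, the CMH sentence refers to outcomes, and van Elteren's test belongs to the same family. A reader might infer that the plan definitely leaves the scores unadjusted for experience; the text does not support that. But the sentence on the scores names only the plain test, and no sentence brings in laterality.
- **Separate judging may mean separate analysis.** If so, one stratified test changes a choice the sponsor has made, and it needs confirmation.
- **The fix does not stratify by surgeon, although randomization does.** True; the two experience groups are coarser but avoid sparse strata and are the plan's own.

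Missing scores do not decide the choice of test. Photographs are taken late ("One to twelve months following implant exchange, 5 photographs"), and the cellulitis definition foresees a case that "or requires surgical removal of implant, but does not contain a purulent fluid collection", so some patients may never be scored. That lowers power for either test: with 300 scored patients the second simulation gives 67.4 → 66.3 at no gaps and 62.9 → 67.4 with both gaps at 0.5 SD. A reader might take this as a further argument against the rank sum test; it is not one.

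**Conclusion.** The point holds as an efficiency and clarity improvement, not as an error. Under the assumed 0.3 SD effect, 199 per arm and complete scoring, four-stratum van Elteren costs under 1 point of power if the strata do not matter. It gains about 0–3 points at a 0.5 SD laterality gap. At 1 SD it gains about 2–4 points with 10% bilateral, about 7–8 with 30% (the two simulated cells give 7.5 and 8.6) and about 9–12 with 50%. For experience gaps up to 0.5 SD, nearly all of the 1 SD gain comes from laterality, and experience adds about 1–2 points at most. Only an experience gap as large as 1 SD would make it matter more.

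Two stronger readings are tempting. One is that pooling biases the comparison or inflates false positives; randomization and the simulated error rates speak against it. The other is that a 1 SD gap reliably costs around 10 points; that depends on a bilateral share which the documents do not give. No stated figure is wrong, and the true gain may be zero.

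**What to change.** Replace the test sentence in the Analysis Plans with, for example:

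> Esthetic scores will be compared by mesh arm with the van Elteren (stratified Wilcoxon) test, stratified by unilateral or bilateral reconstruction and by the surgeon-experience groups of the CMH test (≤3 and >3 years). Overall shape is the main question. Scores will also be summarized separately for unilateral and bilateral patients.

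Add laterality to the recorded variables; section 8.0 already draws operative variables from the operative note, and the surgeon is already recorded. State in section 9.0 whether separate judging refers to the rating or to the analysis. Make the change before scores are seen by arm.

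The cost is a short text change, one data field and under 1 point of power in the worst case under the main assumptions; no extra patients are needed. The statistical downside is that one combined test assumes the mesh effect has the same direction in unilateral and bilateral cases; the separate summaries would show if it does not. If the sponsor intended separate analyses by laterality, this alters that intention and must be confirmed first.

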8.0 Data Collection

All population variables will be collected after enrollment in the study and prior to surgery. After the initial surgery, during which operative variables will be documented by the surgical team, patient data will be collected in clinic. At the postoperative week 1 visit, the patient will be assessed by the surgical team for incisional complications and mastectomy flap necrosis. At the postoperative week 2 visit, expansion will begin, absent complications preventing expansion. The patient will return to clinic for additional expansion, as determined by the a member of the surgical team, until the desired volume is reached. During each of these visits, the patient will be assessed for seroma and infection. After expansion, the patient will return in approximately 3 months for a preoperative visit, followed shortly by tissue expander exchange for a permanent implant. One to twelve months following implant exchange, 5 photographs

(standardized photographic views) will be taken and used for aesthetic evaluation (see Appendix D). Unique study numbers will be assigned to the photographs.

Population variables:

- age
- BMI
- breast size
- past medical history
- smoking history
- tumor size and location
- mastectomy surgeon
- mastectomy method

Operative Variables – These will be collected from the operative note or at the time of surgery:

- plastic/reconstructive surgeon
- tissue expander
- expander type
- quality of skin
- additional skin resection
- intraoperative fill volume
- method of lower pole expansion
- drains

Postoperative Variables – These will be recorded at clinic visits or retrospectively from clinic notes:

- duration of drains
- chemotherapy
- radiation therapy (out of study)
- number of post-op visits
- time to first expansion
- number of expansions
- final fill volume
- time to exchange
- type and volume of implant placed
- contralateral procedures performed
- nipple (yes/no)

9.0 Outcome

The primary endpoint, overall complication after tissue expander implant is defined as any of the following complications: seroma, cellulitis, abscess, red breast syndrome, implant malposition, capsular contracture, and hematoma. These will be defined as follows:

Seroma: Any suspected fluid collection that is either radiologically confirmed by ultrasound or clinically confirmed by drainage, or both.

Cellulitis: Any redness of the breast that resolves with antibiotics, or requires surgical removal of implant, but does not contain a purulent fluid collection.

Abscess: Any purulent fluid collection confirmed during surgical removal of implant.

Red breast syndrome: Any prolonged redness of the breast, without other symptoms of infection, which does not resolve with antibiotics, and does not go on to require removal of the implant.

Malposition: Any surgeon perceived, postoperative movement of the expander outside of the surgically created pocket.

Capsular Contracture: Any postoperative capsule formation, classified according to the Baker classification, as follows: Baker 1: normal breast; Baker 2: palpable, minimally firm capsule; Baker 3: visible, easily palpated, moderately firm capsule; Baker 4: painful, hard and breast distorted.

Hematoma: Any postoperative collection of blood requiring surgical drainage.

Secondary endpoints are related to esthetic evaluation of postoperative, standardized five (5) view clinical photos.

Esthetic Evaluation

The esthetic evaluation will be based on five standardized photographic views: frontal; right lateral; left lateral; right three-quarter: and, left three-quarter. Photographs will be taken against a blue background, standard in all clinic rooms, at a distance of five feet from the patient.

Evaluators will include three attending plastic surgeons who are not taking care of any patients in the study, three plastic surgery fellows, and three physician assistants. Their scores will be averaged for each statement. Unilaterals and bilaterals will be judged separately.

Questionnaires will evaluate the breast esthetics based on a 1 to 5 scale (strongly disagree, disagree, somewhat agree, agree, strongly agree) of the following statements:

1. The overall shape of the reconstructed breast is good.
2. The overall symmetry with the other breast is good.
3. The upper pole transition is natural in appearance.
4. The lower pole has adequate fullness and ptosis.
5. The inframammary fold is in the appropriate position.
6. The lateral border of the breast has good contour.

7. The medial border of the breast has good contour.
8. The breast mound is in the appropriate position.
9. The breast surface contour is generally smooth.
10. There is minimal visible rippling of the implant.

10.0 Number of Patients

Approximately 398 patients will be enrolled in this study.

11.0 Criteria for Removal from the Study

Patients will be removed from the study if they change their mind about participation for any reason.

12.0 Reporting Requirements

Institutional guidelines for reporting of adverse events will be followed.

13.0 Data Confidentiality Plans

The confidentiality of the subjects will be preserved at all times. In no way will any individual subject be identifiable upon discussion or presentation of the data. HIPAA identifiers will be collected but will be replaced by unique study numbers in the analytical file. The data will be stored in a password-protected computer with firewall protection. Data will only be known to the PI and research staff. Study records will be destroyed within five (5) years after study publication.

